8.2. Secondary Immunogenicity Analyses

Not Applicable.

8.3. Exploratory Immunogenicity Analyses

Details of analysis of COVID-19 sequencing and N-Protein Ab ELISA are provided in the SAP and results will be reported in the CSR. Details of other exploratory endpoints such as B cell immune response and SARS-CoV-2 protein-specific T cell responses provided below will not be reported in the CSR but may be reported in a manuscript or other immunogenicity reports.

8.3.2. N-Protein Ab ELISA

Number and percentage of participants with positive N-Protein Ab ELISA among those with available results along with history of N-Protein Ab ELISA results will be reported (Table 48). The number and percentage of participants with reported SARS-CoV-2 positive tests and receipt of COVID-19 vaccine boost outside of the study will be reported in Table 49.

8.3.3. B Cell Immune Response

SARS-CoV-2 specific B cell response to vaccination/boost by analytical flow cytometry will be evaluated for subsets of participants in Cohort 1 Study Groups. Both D614G ("WT") and BA.1 ("Omicron") variant probes will be used to identify WT-specific and cross-reactive cells elicited by vaccination. Summaries (including number of observations, median, IQR and range) will be reported at each timepoint for the following markers of B-cell response:

- Percent S2P WT+ (Total S-2P) of all IgG and IgA memory B cells.
- Percent S2P WT+/S2P Omicron+ (Cross-reactive S-2P) of all IgG and IgA memory B cells.
- Percent S2P WT+/S2P Omicron- (WT-only S-2P) of all IgG and IgA memory B cells.
- Percent RBD WT+ (Total RBD) of all IgG and IgA memory B cells.
- Percent RBD WT+/RBD Omicron+ (Cross-reactive RBD) of all IgG and IgA memory B cells.
- Percent RBD WT+/RBD Omicron- (WT-only RBD) of all IgG and IgA memory B cells.
- Percent S2P NTD WT_Omicron+ (Total NTD) of all IgG and IgA memory B cells
- Percent RBD WT-/NTD WT_Omicron-/S2P WT+ (Total S-2P-only) of all IgG and IgA memory B cells.
- Percent RBD WT-/NTD WT_Omicron-/S2P WT+/S2P Omicron+ (Cross-reactive S-2P-only) of all IgG and IgA memory B cells.
- Percent RBD WT-/NTD WT_Omicron-/S2P WT+/S2P Omicron- (WT-only S-2P-only) of all IgG and IgA memory B cells.
- Percent RBD WT+ or NTD WT_Omicron+ or S2P WT+ (Any Probe) of all IgG and IgA memory B cells.

For B cell response characterization, further subsampling selection will be performed, randomly selecting 12 participants (with 6 per Age Group) among the original subset of 20 participants selected for testing of T cell and live-virus neutralization in each boosting group.

8.3.4. SARS-CoV-2 Protein-Specific T Cell Responses

SARS-CoV-2 CD4+ and CD8+ T cell responses, as obtained from a validated 27-color ICS/Flow cytometry assay, will be reported for a subset of participants. Specimens were stimulated with two peptide pools (15 amino acids overlapping by 11 amino acids) covering the S1 and S2 regions of the original Wuhan strain, along with variant peptides for the D614G mutation. Results for the following markers will be reported:

- Percent of CD4+ Cells Expressing IL-2 and/or IFN-g
- Percent of CD4+ Cells Expressing IL-2 and/or IFN-g and/or CD154
- Percent of CD4+ Cells Expressing IL-4 and/or IL-5/IL-13 and CD154
- Percent of CD8+ Cells Expressing IL-2 and/or IFN-g

Summaries for these markers include number of participants with successfully assayed samples, proportion of participants with positive response and, both overall and among those with positive response, the median, IQR and range of the percent CD4+/CD8+ expressing specific cells.

9. SAFETY EVALUATION

Summaries and analysis of safety data will be presented for the Safety Population. Safety summaries will be presented overall and grouped by study group.

Solicited AEs will be summarized by severity for each day post vaccination (Days 1-8) and as the maximum severity over all 8 days. Solicited AEs that were ongoing beyond Day 8 will be summarized in the Day 8+ and maximum post baseline columns. Additionally, solicited AEs will be analyzed by taking the most severe response over the follow-up period and using standard techniques, such as exact confidence intervals (CI), to summarize the proportion of participants reporting each symptom, any local symptom, and any systemic symptom.

Unsolicited non-serious AEs will be collected from the time of the delayed boost vaccination through 28 days after vaccination. Unsolicited AEs will be coded by MedDRA for preferred term and system organ class (SOC). SAEs, protocol specified AESIs, MAAEs, and NOCMCs will be collected from the time of delayed boost vaccination through the end of planned study participation. The information collected on SAEs, AESIs, NOCMCs, and MAAEs will be reported in detailed listings showing the event description, MedDRA preferred term and SOC, relevant dates (study boost vaccination and onset/resolution of AEs), severity, relatedness, and outcome for each event. Non-serious unsolicited AEs will be summarized as number and percentage of participants reporting at least one event in each MedDRA preferred term and SOC, cross tabulated by severity and relationship to study vaccination. Additionally, the proportion of participants and exact 95% CIs of AEs in aggregate and by MedDRA categories will be computed.

9.1. Demographic and Other Baseline Characteristics

Summaries of age, sex, ethnicity, race, height, weight, and BMI will be presented by study group (Table 10 and Table 11). Age, height, weight, and BMI will be summarized as continuous variables. Ethnicity is categorized as Hispanic or Latino, not Hispanic and not Latino, Not Reported, or Unknown. Race is categorized as American Indian or Alaskan Native, Asian, Black or African American, Native Hawaiian or other Pacific Islander, White, or Other. Participants self-designated as belonging to more than one race are categorized for the analysis as Multi-Racial and participants who refuse to identify a race are categorized as Unknown.

Individual participant listings will be presented for all demographic characteristics collected (Listing 7).

9.1.1. Prior and Concurrent Medical Conditions

Summaries of participants' pre-existing medical conditions will be presented by treatment group (Table 12).

Individual participant listings will be presented for all medical conditions (Listing 8).

9.1.2. Prior and Concomitant Medications

Summaries of medications that were started prior to dosing and continuing at the time of dosing will be presented by WHO Drug Anatomical Therapeutic Chemical (ATC) classification levels 1 and 2 and study group (Table 68). This table will only include medications collected per protocol and meeting the protocol concomitant medications reporting criteria.

Individual participant listings will be presented for all concomitant medications collected in the study including medications that did not meet the reporting criteria will be presented (Listing 16).

9.2. Measurements of Treatment Compliance

Only one study vaccination is expected (delayed boost at least 12 weeks after EUA vaccination). Any participants who were enrolled but not vaccinated will be presented by study group as part of the participant disposition table (Table 7).

9.3. Adverse Events

When calculating the incidence of adverse events (i.e., on a per participant basis), each participant will only be counted once and any repetitions of adverse events within a participant will be ignored; the denominator will be the total population size. All adverse events reported will be included in the summaries and analyses. A summary of all adverse events is provided in Table 50. A summary of those events that occurred in $\geq 5\%$ of participants in any study group is provided in Table 51. Frequency of adverse events will be defined as the total number of adverse events including all repetitions of adverse events within a participant.

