6. GENERAL STATISTICAL CONSIDERATIONS

6.1. General Principles

Unless otherwise specified, all continuous variables will be summarized using the following descriptive statistics: n (non-missing sample size), mean, standard deviation, median, maximum and minimum. The frequency and percentages (based on the non-missing sample size) of observed levels will be reported for all categorical measures. In general, all data will be listed, sorted by study group and participant, and when appropriate by visit number within participant. All summary tables will be structured with a column or row for each study group in the following order:

- Group 4E [Dosed Janssen, Boost Janssen]
- Group 5E [Dosed Moderna, Boost Janssen]
- Group 6E [Dosed Pfizer, Boost Janssen]

All tables will be annotated with the total population size relevant to that table/treatment, including any missing observations.

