6.3.1. Safety Population

The Safety Population includes all participants who received at least one dose of the delayed Janssen-Ad26.COV2.S booster vaccine.

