6.5. Missing Data and Censoring

There will be no imputations planned for missing data. A complete-case analysis approach will be used, and summaries will be reported for participants with non-missing values only.

For binding antibody and FRNT endpoints, values below the lower limit of quantification (LLOQ) will be kept as reported by the corresponding laboratory if actual numerical values are provided. If actual values below the LLOQ are not provided, the observations will be replaced with a value equivalent LLOQ/2. Values that are greater than the upper limit of quantification (ULOQ) will be kept when actual values are reported from the corresponding laboratory. If actual values above the ULOQ are not provided, observations will be replaced with a value equivalent to the ULOQ.

For live-neutralization endpoint, any values below the lower limit of detection (LLOD) will be assigned a value equivalent to one-half the lower limit of detection for analysis purposes, and any values reported as greater than or equal to the upper limit of detection (and no absolute value is available) will be assigned a value equivalent to the upper limit of detection value. Levels that are reported as above the LLOD but below the LLOQ will be kept as reported by the corresponding laboratory if actual numerical values are provided. If a value is reported to be between the LLOD and LLOQ, but the value was not provided, the observations will be replaced with a value equivalent to the midpoint between LLOD and LLOQ (i.e., [LLOD +LLOQ]/2). If actual values below the LLOQ are not provided, the observations will be replaced with a value equivalent to LLOQ will be kept when actual values are reported from the corresponding laboratory. If actual values above the ULOQ are not provided, observations will be replaced with a value equivalent to the ULOQ.

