9.3.1. Solicited Events and Symptoms

Systemic solicited adverse events were collected pre-vaccination, and systemic and local solicited adverse events were collected 30 minutes post-vaccination and then daily for 7 days after vaccination and graded on a scale of 0 (none), 1 (mild), 2 (moderate) and 3 (severe), and 4 (potentially life-threatening). Systemic events include fatigue, headache, myalgia, arthralgia, nausea, chills, and fever. Local events include injection site pain, injection site erythema, and injection site edema/induration. Erythema and induration measurements between 0 and 2.5 cm were reported in the data system as not gradable but will be summarized as having a severity of none since their measurement were below the criteria for mild severity.

The proportion of participants reporting at least one solicited adverse event will be summarized for each solicited adverse event, any systemic symptom, any local symptom, and any symptoms. The 95% CI calculated using Clopper-Pearson methodology from a binomial distribution (SAS Proc Freq with a binomial option) will be presented (Table 52). For each systemic and local event, any systemic event, any local event, and any solicited event, the maximum severity over 7 days after study vaccination will be summarized for the Safety Population. The number and percentage of participants reporting each event will be summarized by the maximum severity and study group. For each event, the denominator is the number of participants with non-missing data for the specific event (Table 52).

The number of participants reporting a solicited adverse event will be summarized for each day post vaccination in a summary table (Table 53, Table 54, and Table 55) and graphically in a bar chart (Figure 69 and Figure 70).

Solicited adverse events by participant will be presented in Listing 10 and Listing 11.

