14.3 Safety Data

14.3.1 Displays of Adverse Events

Table 50:Overall Summary of Adverse Events

	[Dosec Boost	oup 4E l Janssen, Janssen] N=X)	[Dosed Boost	oup 5E Moderna, Janssen] N=X)	[Dose Boost	oup 6E d Pfizer, Janssen] N=X)		rticipants = xx)
Participants ^a with	n	%	n	%	n	%	n	%
At least one local solicited adverse event	x	x	x	x	x	x	x	x
At least one systemic solicited adverse event	x	x	x	x	x	x	x	x
At least one unsolicited adverse event	x	x	x	X	x	x	X	x
At least one related unsolicited adverse event	x	x	x	x	x	x	x	x
Mild (Grade 1)	x	х	х	x	х	x	х	х
Moderate (Grade 2)	x	х	х	x	х	x	x	x
Severe (Grade 3)	x	x	x	x	x	x	x	x
At least one severe (Grade 3) unsolicited adverse event	x	x	x	x	x	x	x	x
Related	x	х	х	х	х	x	x	X
Unrelated	x	x	X	x	X	x	X	X
At least one serious adverse event ^b	x	x	x	x	x	x	x	x
At least one related, serious adverse event	x	x	x	x	X	x	X	x
At least one medically attended adverse event	x	x	x	x	x	x	x	x
At least one new onset chronic medical condition	х	х	х	x	x	x	x	х
At least one adverse event of special interest N = Number of participants in the Safety Population ^a Participants are counted once for each category regardles	s of the pu	mber of ever	nts					

^a Participants are counted once for each category regardless of the number of events. ^b A listing of Serious Adverse Events is included in Table 57.

Adverse Events Occurring in 5% of Participants in Any Study Group by MedDRA Table 51: System Organ Class and Preferred Term, and Study Group - Safety Population

MedDRA System Organ Class	Preferred Term		osed oost J	1p 4E Janssen, [anssen] =X)		osed I Soost J	ıp 5E Moderna, [anssen] =X)	-	Dosed oost J	up 6E l Pfizer, [anssen] =X)	Al		ticipants =X)
		n	%	Events	n	%	Events	n	%	Events	n	%	Events
Any Adverse Event ^a													
All	All	x	х	х	x	х	х	x	x	х	x	х	х
Non-serious Adverse Events					•								
All	All	x	х	х	x	х	x	x	x	x	x	х	х
SOC1	PT1	x	х	х	x	х	х	x	x	х	x	х	х
Etc.	Etc.												
Solicited Adverse Events	•					1	L				L		
All	All	x	х	х	x	х	х	x	x	х	x	х	х
SOC1	PT1	x	х	х	x	х	х	x	х	x	x	х	х
Etc.	Etc.												
N = number of participants in the Sa n= number of participants reporting Events= total frequency of events re Solicited events ongoing past Day 8 ^a Includes only non-serious adverse of	event. ported. are included as unsoli	cited	event	ts.		% three	eshold.		1	1		1	 

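### SAP 9.3 and 9.3.1 give different denominators for solicited events, so Tables 50 and 51 would print lower rates than Table 52 if any boosted participant lacks solicited data

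*SAP*

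**What the plan says.** SAP 9.3 covers the per-participant incidence of adverse events without separating solicited from unsolicited events. It states that "the denominator will be the total population size" and then assigns the displays: "A summary of all adverse events is provided in Table 50", with Table 51 for events reaching 5% in any group.

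The Table 50 shell (SAP Appendix 1, 14.3.1) has n and % for "At least one local solicited adverse event" and for the systemic equivalent. Table 51 has a block of solicited events. The note under Table 50 reads "N = Number of participants in the Safety Population", Table 51 defines N in the same way, and neither shell has a non-missing count. Membership of that population requires only the injection: "The Safety Population includes all participants who received at least one dose of the delayed Janssen-Ad26.COV2.S booster vaccine".

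SAP 9.3.1 gives a different rule for solicited events: "For each event, the denominator is the number of participants with non-missing data for the specific event (Table 52". Table 52 includes rows for any local and any systemic symptom, so it covers the same quantities as the solicited rows of Table 50.

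The general rules agree with 9.3.1. SAP 6.1 says: "The frequency and percentages (based on the non-missing sample size) of observed levels will be reported for all categorical measures". SAP 6.5 rules out imputation and adds: "A complete-case analysis approach will be used, and summaries will be reported for participants with non-missing values only".

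**The concern.** Take a boosted participant with no solicited data at all. Under 9.3 that person stays in the denominator of Tables 50 and 51 and adds nothing to the numerator, which is the same as recording no reaction. Under 9.3.1 the person drops out of Table 52. In effect the 9.3 rule imputes missing as no event, although SAP 6.5 plans no imputation.

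The error can run in one direction only. Table 50 can equal or understate the Table 52 rate but cannot exceed it. Solicited events within 7 days of the boost are part of the co-primary safety endpoint (SAP 3.1), and Table 50 is the overall summary. One clinical study report could therefore carry two rates for the same endpoint. The Table 52 shell gives only the Safety Population N, so a reader could not see why they differ.

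**Working it through.** The plan states no solicited-event percentage and no missing-data rate, so there is no figure of its own to reproduce. The check is the algebra of the two rules, with an illustration.

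**Inputs**
- N = 50 boosted participants per group (SAP 5 and Table 1).
- Tables 50 and 51 denominator: N (SAP 9.3 and the shell footnotes).
- Table 52 denominator: N − m, where m is the number without data for the event (SAP 9.3.1).
- m: not in the documents; assumed 0 to 5. The top value equals the plan's roughly 10% attrition scenario (45 of 50), which is not stated as a loss of seven-day diary data.
- x, the number with an event: assumed.

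**Formulas**
- Table 50 rate = x / N
- Table 52 rate = x / (N − m)
- Ratio of Table 50 to Table 52 = (N − m) / N
- Gap = x·m / [N(N − m)]

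**Illustration with x = 36, N = 50**

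| m | Table 50 | Table 52 | Gap (points) |
|---|---|---|---|
| 0 | 36/50 = 72.0% | 36/50 = 72.0% | 0 |
| 1 | 36/50 = 72.0% | 36/49 = 73.5% | 1.5 |
| 2 | 36/50 = 72.0% | 36/48 = 75.0% | 3.0 |
| 5 | 36/50 = 72.0% | 36/45 = 80.0% | 8.0 |

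SAP 13 rounds percentages to whole numbers, so the pairs for m = 1, 2 and 5 would print as 72 against 73, 75 and 80. The exact 95% interval for 36/45 is 65.4% to 90.4%, so even at m = 5 the 72% lies inside it.

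**Other event counts, m from 1 to 5**
- x = 10: gap 0.4 to 2.2 points
- x = 25: gap 1.0 to 5.6 points
- x = 40: gap 1.6 to 8.9 points

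**What counts as non-missing.** SAP 9.3.1 also collects solicited events 30 minutes after vaccination and does not define non-missing. Suppose five participants return no diary but had an uneventful 30-minute check. If that check counts as data, m = 0 for Table 52, both tables give 36/50 = 72.0%, and the five appear as no reaction in both. If it does not count, Table 52 gives 36/45 = 80.0%. The definition decides whether the five show up as a discrepancy or are absorbed without trace.

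**The case against.** The strongest reply is that 9.3 is the general rule, while 9.3.1 and 9.3.2 set their own denominators for solicited and unsolicited events. With the specific rule overriding the general one, nothing conflicts. This is a reasonable guess at the intent, but the text does not say it: 9.3.1 ties its denominator to Table 52, and 9.3 names Tables 50 and 51. Reading 9.3 as meant for unsolicited events fails too, because 9.3.2 already gives an unsolicited denominator and Table 50 has solicited rows.

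A second reply is that few participants will lack data. Protocol 8.2 requires at least 30 minutes of observation with a reactogenicity assessment before discharge, Memory Aids are reviewed by telephone at one week and again two weeks after the boost, and protocol 9.2.1 expects near-complete safety visits. This stands: the gap may be small or zero.

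A third is that the trial tests no hypothesis, Table 52 already uses the better denominator, and Listings 10 and 11 show individual data. This also stands and limits the weight of the point.

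A reader might infer more than the documents support:
- *That the reported rate will be biased and the tables will contradict each other.* This needs m > 0, and no missing rate is given.
- *That anyone without a diary is absent from Table 52.* The 30-minute check may keep that person in as non-missing.
- *That Figures 69 and 70 or Tables 53 to 55 share the fault.* A displayed N is not a stated percentage denominator: SAP 6.1 requires tables to show the population size including missing observations, and Table 52 itself shows the Safety Population N although its stated denominator is non-missing data.
- *That Table 50 would print a misleading confidence interval.* It has n and % columns only. Nor does the Table 52 shell have a single any-grade row; a reader would take that proportion as the complement of the row for no symptom, although the text of 9.3.1 plans to report it.

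**Conclusion.** The inconsistency is in the text. As written, SAP 9.3 counts boosted participants with no solicited data as reaction-free in Tables 50 and 51, whereas 9.3.1, 6.1 and 6.5 would leave them out. Tables 50 and 51 are then lower than Table 52 by the factor (N − m)/N. In the illustration the gap is 1.5 points with one of 50 missing, 3.0 with two and 8.0 with five; the event count and m are both assumed. If nobody lacks solicited data, or if the 30-minute check counts as data for everyone, the tables agree.

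This should be corrected before the tables are programmed, because it concerns the overall summary of a co-primary endpoint and the correction is cheap. It does not threaten the trial's conclusions.

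**What to change.** 1. In SAP 9.3, limit the total-population denominator to unsolicited AEs, SAEs, AESIs, MAAEs and NOCMCs.
2. State that the solicited rows of Tables 50 and 51 use the 9.3.1 denominator, and print that n in Tables 50, 51 and 52.
3. In SAP 9.3.1, define non-missing as at least one daily Memory Aid assessment after clinic discharge, or any reported event. The 30-minute check alone then does not make a participant reaction-free. The second part of the definition keeps every reported reaction in the numerator. It tilts the rate slightly upward when someone has a reaction at 30 minutes and no diary, so a footnote should give the number of such participants.

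The cost is a few lines of SAP text and a denominator column or footnote in three shells. No new data are needed, and no other display has to change.

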9.3.1. Solicited Events and Symptoms

Systemic solicited adverse events were collected pre-vaccination, and systemic and local solicited adverse events were collected 30 minutes post-vaccination and then daily for 7 days after vaccination and graded on a scale of 0 (none), 1 (mild), 2 (moderate) and 3 (severe), and 4 (potentially life-threatening). Systemic events include fatigue, headache, myalgia, arthralgia, nausea, chills, and fever. Local events include injection site pain, injection site erythema, and injection site edema/induration. Erythema and induration measurements between 0 and 2.5 cm were reported in the data system as not gradable but will be summarized as having a severity of none since their measurement were below the criteria for mild severity.

The proportion of participants reporting at least one solicited adverse event will be summarized for each solicited adverse event, any systemic symptom, any local symptom, and any symptoms. The 95% CI calculated using Clopper-Pearson methodology from a binomial distribution (SAS Proc Freq with a binomial option) will be presented (Table 52). For each systemic and local event, any systemic event, any local event, and any solicited event, the maximum severity over 7 days after study vaccination will be summarized for the Safety Population. The number and percentage of participants reporting each event will be summarized by the maximum severity and study group. For each event, the denominator is the number of participants with non-missing data for the specific event (Table 52).

The number of participants reporting a solicited adverse event will be summarized for each day post vaccination in a summary table (Table 53, Table 54, and Table 55) and graphically in a bar chart (Figure 69 and Figure 70).

Solicited adverse events by participant will be presented in Listing 10 and Listing 11.

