8.2 Safety and Other Assessments

Study procedures are specified in the SOA. A study clinician, licensed to make medical diagnoses and listed on the Form FDA 1572 as the participating site PI or appropriate sub-investigator, will be responsible for all study-related medical decisions.

Medical history:

A complete medical history will be obtained by interview of subjects at the screening (optional) or enrollment/baseline visit. Subjects will be queried regarding a history of significant medical disorders.

At all subsequent visits an interim medical history will be obtained by interview of subjects and any changes since the previous clinic visit or telephone call will be noted. The interim medical history should include an assessment to identify intercurrent Protocol Specified AESIs, MAAEs, and NOCMCs.

Physical examination:

A symptom-directed (targeted) physical examination will be performed if indicated at any timepoint at the discretion of the participating site PI or appropriate sub-investigator, if necessary, to evaluate AEs.

Reactogenicity assessments of solicited AEs, occurring from the time of each vaccination through 7 days post vaccination, will include an assessment of injection site reactions—erythema, edema/induration and pain, as well as systemic reactions—fever, fatigue, chills, myalgia (exclusive of the injection site), arthralgia, headache, and nausea. Pre-administration reactogenicity assessments will be performed immediately prior to each vaccination to establish baseline, then the vaccination will be given.

Subjects will be observed in the clinic for at least 30 minutes post each vaccination. The vaccination site will be examined, post-administration reactogenicity assessments will be performed, and any AEs/SAEs will be recorded on the appropriate DCF prior to discharge from the clinic. The vaccination site will also be examined 7 days after vaccination.

Vital signs: Vital sign measurements will include systolic and diastolic BP, HR, and oral temperature. Vital signs will be measured at timepoints specified in the SOA. On vaccination days, vital sign measurements will be collected prior to vaccine administration. Vital signs assessed on Day 1 prior to the first vaccination will be considered as baseline. Subjects must not eat or drink anything hot or cold within 10 minutes prior to taking oral temperature.

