8.3 Adverse Events and Serious Adverse Events

8.3.1 Definition of Adverse Event (AE)

AE means any untoward medical occurrence associated with the use of an intervention in humans, whether or not considered intervention-related [21 CFR 312.32 (a)]. An AE can therefore be any unfavorable and unintended sign, symptom or disease temporally associated with the use of medicinal (investigational) product.

Any medical condition that is present at the time that the subject is screened will be considered as baseline and not reported as an AE. However, if the severity of any pre-existing medical condition increases, it should be recorded as an AE.

AEs can be further divided into solicited AEs and unsolicited AEs. Solicited AEs are those for which the study team will specifically query the subject whether they occurred. Unsolicited AEs are those events that the subject report occurring without being queried about the specific event.

All AEs will be assessed for severity and relationship to study intervention ([Section 8.3.4](#)). Reporting of all AEs, solicited and unsolicited, will occur during the period from study product administration on Day 1 through 28 days after each vaccination. After 28 days post last vaccination through the end of planned study participation, only SAEs, Protocol Specified AESIs, MAAEs, and NOCMCs will be reported as AEs.

All AEs, solicited and unsolicited, will be captured on the appropriate DCF. Solicited AEs will be regarded as related to the study product and will not require separate entry into the AE log. Information to be collected for unsolicited AEs includes event description, date of onset, assessment of severity, relationship to study product and alternate etiology (assessed only by those with the training and authority to make a diagnosis and listed on the Form FDA 1572 as the participating site PI or appropriate sub-investigator), date of resolution, seriousness, and outcome. AEs occurring during the study-collection and reporting period will be documented appropriately regardless of relationship.

AEs will be followed to resolution or stabilization.

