8.3.4.2 Relationship to Study Intervention

For each reported adverse reaction, the participating site PI or qualified designee must assess the relationship of the event to the study product using the following guidelines:

Related – The AE is known to occur with the study intervention, there is a reasonable possibility that the study intervention caused the AE, or there is a temporal relationship between the study intervention and event. Reasonable possibility means that there is evidence to suggest a causal relationship between the study intervention and the AE.

Not Related – There is not a reasonable possibility that the administration of the study intervention caused the event, there is no temporal relationship between the study intervention and event onset, or an alternate etiology has been established.

Solicited adverse events reported in the 7 days after each vaccination are considered related to study product unless they are also recorded as an unsolicited event, in which case the relationship to study product will be determined by the PI or qualified designee.

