Severity is the ma ^a Day 8+ includes ^b Indicates how m these categories.	er of participants in the Safety Pop aximum severity reported post dos s the maximum severity of each sy any participants had "None", "Mi rythema measurements graded bas	ing for mptom ld", "M	each p report Ioderat	ed on o e", "Se	r after I vere", o	Day 8 (or "Pote	include entially	Life-t	hreaten	ing" as	their r			-	-				-			e than c	one of

Tables with similar format:

- Table 54:Summary of Solicited Events by Days Post Delayed Boost Vaccination and Symptom Study Group 5E [Dosed Moderna, Boost
Janssen], Safety Population
- Table 55:Summary of Solicited Events by Days Post Delayed Boost Vaccination and Symptom Study Group 6E [Dosed Pfizer, Boost
Janssen], Safety Population

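### Table 52 counts systemic symptoms after the booster without regard to the participant's own pre-dose grade, so symptoms that were already present and did not worsen enter the solicited AE rates

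*SAP*

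**What the plan says.** Protocol 8.2 explains why symptoms are graded before the dose: "Pre-administration reactogenicity assessments will be performed immediately prior to each vaccination to establish baseline". SAP 9.3.1 confirms which grades exist: "Systemic solicited adverse events were collected pre-vaccination". Local symptoms are collected only after the injection.

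The estimates use post-dose grades alone. SAP 9 says that "solicited AEs will be analyzed by taking the most severe response over the follow-up period", with exact confidence intervals. SAP 9.3.1 says that "the maximum severity over 7 days after study vaccination will be summarized for the Safety Population", and the Table 52 footnote likewise refers to severity after dosing. The shell for Table 53, reused for Tables 54 and 55, has a pre-dose column by symptom and severity beside the post-dose columns.

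On what counts as an event, protocol 8.3.1 treats a medical condition present at screening as baseline and not an AE, but adds that "if the severity of any pre-existing medical condition increases, it should be recorded as an AE". The same section says "Solicited AEs will be regarded as related to the study product". Protocol 8.3.4.2 qualifies this: solicited events in the 7 days after vaccination "are considered related to study product unless they are also recorded as an unsolicited event", in which case the investigator or a designee judges the relationship.

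**The concern.** A baseline is measured, but the main rates do not use it. Take a participant with Grade 1 arthralgia before the injection and Grade 1 arthralgia for the following week. Table 52 counts this person as having mild arthralgia after the booster. By default the event is regarded as related, although protocol 8.3.1 would not call an unchanged pre-existing condition an AE. The SAP does not say how that baseline rule applies to solicited symptoms.

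The design makes this more important than it would be in a controlled trial. Solicited events are a primary endpoint. There is no placebo group (protocol 4.2), so background fatigue, headache or joint pain cannot be read off a control arm, and the participant's own pre-dose grade is the only internal reference. Groups 4E, 5E and 6E are not randomised (protocol 6.3.2), so nothing in the design balances pre-dose prevalence between columns shown side by side. Some baseline symptoms are plausible: stable pre-existing disease is allowed, about 25 of each 50 participants are 56 or older, and afebrile minor illness may be enrolled at the investigator's discretion.

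**Working it through.** **The plan's own safety figure.** SAP 5 gives a 99.5% chance of seeing at least one AE with a true rate of 10% when n = 50. The check is 1 − 0.9^50 = 0.9948, which reproduces it. The n = 25 figure also reproduces: 1 − 0.9^25 = 0.9282, stated as 92.8%. These figures are not in dispute. The documents contain no figure for pre-dose prevalence.

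**Direction.** A participant whose post-dose maximum exceeds the pre-dose grade has a post-dose grade of at least 1, so Table 52 already counts that participant. Table 52 also counts those whose post-dose grade is at least 1 but no higher than pre-dose. In the same participants, the Table 52 rate can therefore never be below the new-or-worsened rate. A pre-dose symptom that is not reported again after the dose adds nothing.

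**Size.** All three inputs below are assumptions.

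- r: proportion with a new or worsened symptom
- p0: proportion with the symptom pre-dose
- k: share of those in whom it is reported after the dose without worsening

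Treating the two sources as independent:

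reported rate = 1 − (1 − r)(1 − p0·k)

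excess over r = (1 − r)·p0·k

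For r = 15%, p0 = 10% and k = 1: 0.85 × 0.10 = 8.5 points, so 15% is reported as 23.5%. In a group of 50 this is 0.085 × 50 = 4.25 participants. For p0 = 2% it is 0.85 × 0.02 = 1.7 points, or 0.85 of a participant.

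Excess in percentage points with k = 1 (halve every entry for k = 0.5):

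| r | p0 = 2% | p0 = 5% | p0 = 10% |
|---|---|---|---|
| 10% | 1.8 | 4.5 | 9.0 |
| 15% | 1.7 | 4.25 | 8.5 |
| 30% | 1.4 | 3.5 | 7.0 |
| 50% | 1.0 | 2.5 | 5.0 |
| 70% | 0.6 | 1.5 | 3.0 |

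The excess is largest for the less common symptoms.

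**Against sampling error.** The Clopper-Pearson 95% interval is 17.9% to 44.6% for 15/50 and 35.5% to 64.5% for 25/50, half-widths of about 13 and 15 points. The excesses above are smaller than that. They all lie in one direction, however, and the interval does not reflect them.

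**The case against.** The strongest reply is that the SAP estimates what the protocol asks for. The endpoint is solicited events in the 7 days after the boost, and protocol 9.4.4 itself specifies severity by day and the maximum over all 8 days. New or worsened relative to pre-dose is a different estimand. This stands, and it is why the existing summary should stay.

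A reader might infer that the pre-dose grades are never used. They are: Tables 53 to 55 show their prevalence by symptom, severity and group. What those columns cannot show is which post-dose reports come from the same participants. Listing 10 is by participant, but its time column is headed as post-dose day, so the shell does not confirm that pre-dose rows will appear.

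A reader might also infer a plain contradiction with the protocol's baseline rule. That rule concerns medical conditions present at screening. It does not say that a dose-day symptom grade offsets later memory-aid reports. If sites do apply it to solicited symptoms, some of the excess is already removed. The documents leave the question open.

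The relatedness point is limited. Protocol 8.3.4.2 provides a route for the investigator's judgement, though only for events also recorded as unsolicited. The solicited rows of Table 50 make no relatedness claim, so that table contains no vaccine-related rate to replace.

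Finally, participants must be in good health, and people who are acutely ill or febrile are not dosed until rescheduled. This largely protects fever. It gives less protection for chronic headache, arthralgia or fatigue, whose pre-dose prevalence is unknown.

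**Conclusion.** The point holds as a gap in the summary, and the remedy is an inexpensive improvement. The Table 52 incidences and exact intervals ignore a baseline that the protocol collects, so an unchanged persisting systemic symptom is counted. Relative to a new-or-worsened rate, the effect can only be upward. It is confined to systemic symptoms that persist or recur after the dose.

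The size is not established. The range of 1.7 to 8.5 points at r = 15% assumes pre-dose prevalence of 2% to 10%, full persistence and independence. With half persistence it is 0.85 to 4.25 points. A reader might go further and conclude that the reactogenicity rates as a whole are inflated by a known amount. The documents do not support this: they give none of r, p0 or k, and local symptoms are untouched. The trial's own data will show the actual difference.

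Neither rate isolates a vaccine effect. A background symptom that begins in the week after the injection is counted in both.

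**What to change.** Keep the post-dose maximum as the main summary, leave the existing Table 50 row in place, and state in SAP 9.3.1 that this summary counts symptoms irrespective of the pre-dose grade. Then add the following to SAP 9.3.1 and Table 52:

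- For each systemic symptom, the number, percentage and Clopper-Pearson 95% interval of participants whose maximum post-dose grade exceeds their own pre-dose grade for that symptom.
- A row for any systemic symptom, new or worsened, defined as at least one individual symptom exceeding its own pre-dose grade. Do not compare the overall maximum with the overall pre-dose maximum: a participant with persisting Grade 1 fatigue and new Grade 1 chills would score 1 against 1 and be missed.
- Participants without a pre-dose grade are excluded from these rows, and their number is shown.

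The cost is one derived flag per symptom from data already collected, and a few extra rows. The drawback is that a symptom that resolves and recurs at the same grade is not counted in the supplementary rows. The existing rows stay for that reason.
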